8.2.2.3.2. Vital Signs

Each vital sign parameter and change from baseline for each vital sign parameters will be summarized by visit for both pre-dialysis and post-dialysis measurements. Vital sign parameters will also summarized with respect to whether the observed values are of potential clinical importance at any time on-therapy.

A plot of mean and 95% CI for systolic and diastolic blood pressure by visit will be created for both pre-dialysis and post-dialysis measurements.

A by-subject listing of vital signs for all subjects and a listing of all vital signs for subjects with any value of potential clinical importance will be produced.

8.2.2.3.3. Hepatobiliary (Liver)

Liver monitoring/stopping event reporting will be summarized by treatment group and Dapro Total. A summary of hepatobiliary laboratory abnormalities will be displayed.

The following graphical displays will be created for liver function tests (LFT):

- box plots over time,
- matrix display of maximum LFT values
- LFT subject profiles. (Note: include subjects who have normal baseline, but have any LFT outside normal range any time post-baseline. LFT subject profiles will include a separate line for dose.)

In addition, the following listings will be created:

- Listing of Liver Event Results and Time of Events Relative to Treatment
- Listing of Past and Current Liver Disease Medical Conditions
- Listing of Alcohol Intake at Time of Liver Event
- Listing of Laboratory Data from Liver Event Follow-Up

8.3. Pharmacokinetic Analyses

8.3.1. Overview of Planned Pharmacokinetic Analyses

The pharmacokinetic (PK) analyses will be based on the Pharmacokinetic population, unless otherwise specified.

Table 8 provides an overview of the planned analyses, with full details being presented in Appendix 14: List of Data Displays.

Table 8 Overview of Planned Pharmacokinetic Analyses

Endpoint / Parameter/ Display Type	Untransformed						Log-Transformed							
	Stats Analysis			Summary		Individual		Stats Analysis			Summary		Individual	
	T	F	L	T	F	F	L	T	F	L	T	F	F	L
GSK1278863 and Metabolites														
GSK1278863 and Metabolites Plasma Pharmacokinetic Concentration Time Data (ng/ml)				Y	Y ¹								Y ¹	
Individual GSK1278863 and Metabolites Plasma Concentration-Actual Time Plot by Treatment						Y								Y
GSK1278863 and Metabolites Plasma Pharmacokinetic Parameter Data	Y			Y			Y	Y			Y			Y

NOTES :

- T = Table, F = Figure, L = Listings, Y = Display generated.
- Stats Analysis = Represents TFL related to any formal statistical analyses (i.e. modelling) conducted.
- Summary = Represents TFL related to any summaries (i.e. descriptive statistics) of the observed raw data.
- Individual = Represents FL related to any displays of individual subject observed raw data.

1. Mean and Median Plots will be generated.

8.3.2. Drug Concentration Measures

Daprodustat (GSK1278863) and metabolites [GSK2391220 (M2), GSK2499166 (M4), GSK2531403 (M3), GSK2531400 (M13), GSK2531399 (M5), and GSK2531398 (M6)] plasma pharmacokinetic concentration will be summarized by visit and planned collection time point for each dose level of daprodustat, and will be listed. Standard summary statistics will be calculated (i.e. mean, standard deviation, median, minimum and maximum). The merge of PK concentration data, randomization and CRF data will be performed by statistical programmers.

Pharmacokinetic data will be presented in graphical and/or tabular form and will be summarized descriptively. Figures for individual plasma concentrations will be presented

on both a linear and semilog scale daprodustat, and its six predominant metabolites. Linear and semi-log figures for mean and median plasma concentrations versus time for each treatment regimen will also be generated.

Overlaid individual plasma concentration-actual time profiles and median/mean plasma concentration-planned time profiles by dose level at visit will be plotted. All plots will include PK data from all visits on the same plot. Each of the figures will contain one plot on the untransformed scale (i.e. a linear plot) and one plot on the log transformed scale (i.e. log-linear plot).

8.3.3. Pharmacokinetic Parameters

Plasma concentration-time data for daprodustat and its six metabolites (GSK2391220 (M2), GSK2506104 (M3), GSK2487818 (M4), GSK2506102 (M5), GSK2531398 (M6), GSK2531401 (M13)) will be analyzed by non-compartmental methods with Phoenix[®] WinNonlin 6.3 or higher (Pharsight Corporation, St. Louis, MO). The data from each PK sampling day will be combined to generate a single profile, i.e., PK concentration data from Days 1, 15 and 29 (taken at non-overlapping time points on these days) will be combined with the actual times, normalized to a 24 hour period to create a “Day 1” profile for non-compartmental analysis (NCA). The exposure estimates obtained from such an analysis will be a close approximation as compared to sampling a subject over a single 24 hour period with minimal patient inconvenience.

Pharmacokinetic parameters described in [Table 9](#) will be determined from the plasma concentration-time data for daprodustat and its six predominant metabolites (GSK2391220 (M2), GSK2506104 (M3), GSK2487818 (M4), GSK2506102 (M5), GSK2531398 (M6), GSK2531401 (M13)), as data permits.

Table 9 Derived Pharmacokinetic Parameters

Please refer to GSK “SOP_00000314000 - 1.0, Non-Compartmental Analysis of Clinical Pharmacokinetic Data, CPMS Global” for calculating PK parameters.

Parameter	Parameter Description
AUC(0-t)	Area under the concentration-time curve from time zero to the time of the last quantifiable concentration (C(t)) will be calculated using the linear trapezoidal rule for each incremental trapezoid and the log trapezoidal rule for each decremental trapezoid.
AUC(0-∞)	Area under the concentration-time curve extrapolated to infinity will be calculated as: $\text{AUC} = \text{AUC}(0-t) + C(t) / \lambda_z$
Cmax	Maximum observed concentration, determined directly from the concentration-time data.
tmax	Time to reach Cmax, determined directly from the concentration-time data.
t _{1/2}	Apparent terminal half-life will be calculated as: $t_{1/2} = \ln 2 / \lambda_z$

NOTES:

- λ_z is the terminal phase rate constant.

All pharmacokinetic endpoints will be summarized in tabular form. Descriptive statistics (n, arithmetic mean, standard deviation, minimum, median, maximum) will be calculated for all pharmacokinetic endpoints by regimen. In addition, for AUC, C_{max} , $t_{1/2}$, geometric means and geometric CVs (CVb(%)) will be calculated for each regimen. Geometric mean and geometric CV% will not be calculated for t_{max} . A subject listing of individual PK parameters for each treatment group will be provided. Pharmacokinetic parameters will be summarized by treatment group using descriptive statistics.

8.4. Pharmacokinetic / Pharmacodynamic Analyses

The relationship between plasma concentrations of daprodustat and selected endpoints may be explored using appropriate pharmacokinetic/pharmacodynamic models. Exploratory modeling of the plasma EPO, VEGF and/or hepcidin concentrations also may be conducted, as a function of daprodustat dose or PK, and may be used to further characterize the effect of daprodustat. Other PD data such as iron parameters and RBC indices may also be included if relevant to characterize the PD response. Relevant measures of the secondary and exploratory endpoints (if meaningful) will be initially explored graphically and where appropriate modeling approaches will be used. Pharmacokinetic/Pharmacodynamic exploratory analysis will be the responsibility of CPMS. If additional details are needed, they will be included in a separate PK/PD RAP. The results of the PK/PD analyses may be reported in separate PK/PD report(s).

9. OTHER STATISTICAL ANALYSES

No other statistical analyses are planned.

11.1. Appendix 1: Protocol Deviation Management and Definitions for Per Protocol Population

11.1.1. Important Protocol Deviation

All deviations are to be tracked in PPD CTMS. PPD is responsible for collating all identified deviations and, after internal review, for sending this list to GSK on monthly basis. Protocol deviations will be reviewed by PPD and GSK study team and important/significant protocol deviations will be identified according to PPD's Study Deviation Rules Document. (Note: Given that different terminologies have been used by GSK and PPD, the terms "important protocol deviation" and "significant protocol deviation" will be used interchangeably throughout the RAP.)

11.1.2. Exclusions from Per Protocol Population

The following criteria define the protocol deviations, which may lead to the exclusion of a subject from the per protocol (PP) population (refer to Section 4 for population definitions). These are the deviations that are considered to affect interpretation of the primary endpoint (Hgb change from baseline at Day 29). Protocol deviations will be recorded and documented in the PPD's protocol deviation capturing tool. Potential protocol deviations listed below will be reviewed by the clinical team to establish whether subjects meeting these criteria should be excluded from the PP population. This review will occur before the clinical database has been locked for the final analysis.

Number	Exclusion Description
01	Inclusion/Exclusion criteria not met. 
 Subjects who deviate from any inclusion or exclusion criteria, as recorded in the eCRF)
02	Not withdrawn after meeting the following stopping criteria prior to Day 29 
 receiving blood transfusion receiving kidney transplant having active GI bleed liver stopping criteria patient not discontinued from the study treatment despite having missed two or more consecutive dialysis sessions diagnosis of cancer, with the exception of squamous cell and basal cell carcinoma pregnancy
03	Prohibited medication taken during study treatment phase, prior to Day 29 
 Subject taking single dose of long-acting darbepoetin or Mircera during the study (Day 1 – Day 29) Subject taking more than one dose of Epoetin, or more than 2 non-consecutive Epoetin administrations

Number	Exclusion Description
	
 Subject taking the prohibited medications (inhibitor or inducer of CYP2C8: gemfibrozil and rifampin/rifampicin) during the 29-day study treatment phase and 7 days after last dose of study treatment).
04	
Incorrect study treatment or Non- compliance
 
 Dispensed incorrect study treatment at Day1 Incorrect bottle used for administration to the patient Expired study drug administered to the patient Administration of study drug that was incorrectly stored and was not approved by GSK for use (Study drug stored incorrectly/ temperature monitoring not documented/ storage temperature excursion) Non-compliance for IP (defined as < 80% or > 120%; refer to RAP Section 6.2.6 for treatment compliance definition) for any single bottle of study treatment between Day 1 and Day 29. Note: <80% is equal to 3 or more doses over 29 days Two or more consecutive missed doses, or 3 or more non-consecutive missed doses Patient takes more than the scheduled number of tablets or doses of Study treatment, e.g. more than 3 tablets per dose or more than 3 doses per week. Patient did not receive one tablet from each of 3 bottles (e.g., took 3 tablets from single bottle).
05	
Error in Randomization procedure
 
 Subject randomized in error. (This should capture any protocol deviation which is not covered by another protocol deviation category such as deviation to eligibility criteria.) 
(Note: Randomization to incorrect stratum will not lead to the exclusion of a subject from the per protocol (PP) population.)

06	
Other (lack of PI oversight)
 
 Exclude subject(s) if failed audit/compliance
07	
If Day15 visit or Day 29 visit is done on first dialysis session of the week (we would check each patient's estimated dry weight (EDW) to see if there is a greater than 4% difference in EDW between the first dialysis session of the week and the dialysis session at mid or end of the week).

08	
Informed Consent
 
 Patient not consented prior to screening procedure ICF not properly completed (Consideration should be given to whether the ICF was later completed properly, and whether a valid consent was in place.) Patient not consented with a current ICF version (e.g. inappropriate re-consenting

Number	Exclusion Description
	process). (Consideration should be given to what new information is contained in the revised ICF, and whether any procedures/assessments were performed to which the subject had not given consent, as a result of not using a current ICF version.)
09	Dialysis modality changed from hemodialysis (HD, hemofiltration or hemodiafiltration) to peritoneal dialysis during the study

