7. STUDY ASSESSMENTS AND PROCEDURES

Protocol waivers or exemptions are not allowed with the exception of immediate safety concerns. Therefore, adherence to the study design requirements, including those specified in the Time and Events Table (Section 7.1), are essential and required for study conduct.

Time and Events Tables are provided in Section 7.1 for the overall study and for the specific Pharmacokinetic/Pharmacodynamic assessments (Table 2).

Study visit days are based on the schedule for hemodialysis as follows:

- Three times weekly: Hgb levels may have the greatest variability around study visits at the beginning of the week; therefore, the Day 1, 15 and 29 study visit must not occur on the first dialysis session of the week (e.g., if Monday-Wednesday-Friday dialysis schedule, then the study visit cannot be on Monday).
- **Four to five times weekly:** Designated study visit can be on any hemodialysis session of the week.

To allow scheduling flexibility, study visits should occur within a window of ± 2 days, except for subjects on a three times weekly dialysis schedule for whom study visits must not be scheduled on the first dialysis session of the week. Post-randomization visits should be referenced back to the Randomization visit (Day 1). In exceptional circumstances, minor changes to visit structure may be permitted after consultation with the GSK Medical Monitor.

The following points must be noted:

- If assessments are scheduled for the same nominal time, **THEN** the assessments should occur in the following order:
 - 1. 12-lead ECG
 - 2. Vital signs

3. Blood draws

NOTE: The timing of the assessments should allow the blood draw to occur at the exact nominal time.

- The change in timing or addition of time points for any planned study assessments must be documented in a Note to File which is approved by the relevant GSK study team member and then archived in the study sponsor and site study files, but this will not constitute a protocol amendment.
- The IRB/IEC will be informed of any safety issues that require alteration of the safety monitoring scheme or amendment of the Informed Consent Form.
- No more than 500 mL of blood will be collected over the duration of the study, including any extra assessments that may be required.

7.1. **Time and Events Table**

Protocol Activity 1,2	Screening			Treatment Period				Follow-up
110.00017.0.0015	Week -4	Week -2	Day 1	Day 15	Day 29	Un-scheduled	Early Withdrawal	Day 43 ± 3 6

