9.2. Sample Size Considerations

No formal sample size and power calculations were performed because the focus of this study is on characterizing the Hgb-three-times weekly dose-response relationship and using the results to estimate the dose ratio between three-times weekly and QD doses that produce the same Hgb response, not on formal testing of hypotheses. A sample size of approximately 90 randomized subjects has been determined based on feasibility (18 per arm).

Assuming a maximum dropout rate of 15% between randomization and Day 29, it is anticipated that approximately 75 subjects will complete 29 days treatment.

Subjects will be stratified by prior ESA dose (low, high), and then randomized in equal proportions to receive placebo three-times weekly, or GSK1278863 dose of 10 mg three-times weekly, 15 mg three-times weekly, 25 mg three-times weekly, or 30 mg three-times weekly.

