2. SUMMARY OF KEY PROTOCOL INFORMATION

2.1. Changes to the Protocol Defined Statistical Analysis Plan

Any changes from the originally planned statistical analysis specified in the protocol are outlined in [Table 1](#).

Table 1 Changes to Protocol Defined Analysis Plan

Protocol	Reporting & Analysis Plan	
Statistical Analysis Plan	Statistical Analysis Plan	Rationale for Changes

 For Hgb Day 1 measurement using central lab Quest will serve as the baseline value. (Section 7.3) 	
 For Hgb the average of Hgb measured by the central lab, Quest, at Week -2 and Day 1 visits will serve as the baseline value. 	
 Average of Hgb measured by the central lab, Quest, at Week -2 and Day 1 visits will reflect the overall pre-treatment stable Hgb level.

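### Per-protocol item 07 names Day 15, which has no weight in an observed Day 29 change, and omits both baseline visits; item 03's CYP2C8 window runs past the endpoint

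*SAP*

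**What the plan says.** - **Purpose of the list.** SAP 11.1.2 describes the listed deviations as those thought to affect interpretation of the primary endpoint. They are candidates for exclusion, reviewed by the clinical team before database lock.
- **Item 07.** It applies "If Day15 visit or Day 29 visit is done on first dialysis session of the week". A parenthesis adds a check for a difference of more than 4% in estimated dry weight between the first and later sessions. It does not mention dialysis schedule.
- **Visit rule.** Protocol section 7 states, for three-times-weekly dialysis, that "the Day 1, 15 and 29 study visit must not occur on the first dialysis session of the week". Protocol 5.1 applies the same ban to the Hgb values at Day -28, Day -14 and Day 1. Subjects dialysed four to five times weekly may attend at any session.
- **Baseline.** SAP 2.1 says that the average of central-laboratory Hgb "at Week -2 and Day 1 visits will serve as the baseline value"; SAP 11.5.2.1 repeats this.
- **Use of Day 15.** Under SAP 11.7.2.1, a missing Day 29 change is imputed as twice the difference between Day 15 Hgb and baseline.
- **Item 03.** Its heading covers prohibited medication before Day 29. The CYP2C8 bullet runs "during the 29-day study treatment phase and 7 days after last dose of study treatment". The epoetin bullet reads "Subject taking more than one dose of Epoetin, or more than 2 non-consecutive Epoetin administrations".
- **Use of PP.** SAP section 4 makes PP a sensitivity population, not analysed if it exceeds 80% of ITT.

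**The concern.** Item 07 does not follow its own stated purpose. It lists a visit that usually plays no part in the primary value and leaves out two visits that always do. Protocol section 7 names Day 1 in the same sentence as Days 15 and 29, so item 07 would have missed a baseline visit even under the protocol's Day 1 baseline. The SAP's move to a two-visit baseline widened the gap.

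Item 03's CYP2C8 window has a related fault, because it counts drug use after the endpoint has been measured. At stake is the value of the PP analysis as a check on the primary model: it can set aside sound values, keep values with a disturbed baseline, and move the count that decides whether PP is run.

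**Working it through.** **1. The plan's own figure.** Protocol 9.2 says "No formal sample size and power calculations were performed", so the point rests on no power figure. For scale: "Assuming a maximum dropout rate of 15% between randomization and Day 29" and 90 randomized give 90 × 0.85 = 76.5, against about 75 stated.

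**2. Weight of each visit.** With H for Hgb:

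- Day 29 observed: change = H(29) − [H(−2) + H(1)] / 2
- Day 29 imputed: change = 2 × {H(15) − [H(−2) + H(1)] / 2} = 2·H(15) − H(−2) − H(1)

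| Visit | Weight, observed | Weight, imputed | Named in item 07 |
|---|---|---|---|
| Week -2 | −0.5 | −1 | No |
| Day 1 | −0.5 | −1 | No |
| Day 15 | 0 | +2 | Yes |
| Day 29 | +1 | not used | Yes |

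The planned PP efficacy displays (SAP Tables 2.7 and 2.10) are the Day 29 Emax and linear models. The repeated-measures model, which does use Day 15, is planned on ITT (Table 2.29).

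**3. Error per subject.** Assume a first-session draw lowers Hgb by d. The documents do not give d; take 0.25 to 1.0 g/dL.

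- Day 15 breach, Day 29 observed: 0
- Day 29 breach: −d, or −0.25 to −1.0
- Week -2 or Day 1 breach alone: +d/2, or +0.125 to +0.5
- Both baseline visits: +d, or +0.25 to +1.0
- Day 15 breach, Day 29 imputed: −2d, or −0.5 to −2.0

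**4. Possible counts.** Assume 90 subjects, all on three-times-weekly dialysis, independent breaches at rate q per visit, and a fraction m of 0 to 15% with Day 29 missing.

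- Flagged with no used visit affected: 90(1−m)q(1−q)³
- Affected baseline but not flagged: 90[1−(1−q)²] × [(1−m)(1−q)² + m(1−q)]

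| q | Flagged needlessly | Affected, not flagged |
|---|---|---|
| 5% | 3.3 to 3.9 | 7.9 to 8.0 |
| 10% | 5.6 to 6.6 | 13.9 to 14.1 |
| 20% | 7.8 to 9.2 | 20.7 to 21.5 |

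These counts ignore the dry-weight check, the clinical review and item 01, so they describe item 07 read literally.

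**5. Mean shift.** If Day 1 alone is breached in a share q of subjects, the mean change moves by q·d/2. From 0.05 × 0.25/2 to 0.20 × 1.0/2 this is 0.006 to 0.10 g/dL. At the protocol's slope of about 0.05 g/dL per mg it equals about 0.1 to 2.0 mg, against target-dose half-widths of 2.86 and 5.94 mg in protocol Table 4. If both baseline visits were breached in 20% at d = 1.0, the figures are 0.20 g/dL and 4.0 mg; that corner exceeds the smaller half-width.

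**6. Item 03.** A last dose on Day 29 takes the CYP2C8 window to Day 36. A Day 29 Hgb sample cannot reflect use on Days 30 to 36. On-treatment laboratory data end one day after the last dose (SAP 11.4.2.1). For epoetin, two doses already meet the first clause, and any count above two also exceeds one. The second clause therefore never adds a subject.

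**7. The 80% rule.** With 90 in ITT, PP is analysed only at 72 or fewer (18 or more excluded); with 75, at 60 or fewer (15 or more excluded).

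**The case against.** **Nothing on the list excludes anyone automatically.** Clinical review comes first, and the dry-weight check may narrow item 07 to visits with a real fluid difference. This stands. A reader might infer that the PP set will remove and keep the wrong subjects; the documents support only that it can. But the review is of the listed deviations, so a baseline breach not on the list has no stated route to it. The SAP also does not say whether the dry-weight check is a condition of exclusion.

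**Baseline breaches may be caught elsewhere.** Inclusion criterion 2 refers to protocol 5.1, so item 01 may apply, and item 05 covers subjects randomized in error. This partly stands. Item 01 depends on the eCRF record, and protocol 5.1 describes an automatic check of Hgb values without mentioning the dialysis session.

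**Day 15 matters.** It has weight 2 when Day 29 is imputed, and protocol 5.6.2 uses the two-week Hgb change in its discontinuation rule. Both are correct, so deleting Day 15 from item 07 would be wrong. A subject stopped at Day 15 with no on-treatment Day 29 value would be imputed from Day 15, so a condition tied to imputation still reaches that subject.

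**The CYP2C8 window copies the protocol.** Protocol 6.9.2 does prohibit these drugs for seven days after the last dose. That explains the wording but does not make later use relevant to an Hgb already drawn.

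**The epoetin clause is harmless.** As written it excludes nobody extra. A reader might take item 04's split between consecutive and non-consecutive doses as proof of what was meant; that is inference.

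**Conclusion.** The point holds as a minor inconsistency in the PP definition. Item 07 can flag a subject whose primary value is untouched and does not name the two visits behind every baseline. Item 03's CYP2C8 window passes both its own heading and the endpoint. The weights follow directly from the SAP; the sizes rest on assumed values of d and q. A single affected baseline visit moves an individual change by 0.125 to 0.5 g/dL under those assumptions. The mean shift with Day 1 alone affected is at most 0.10 g/dL.

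A reader might go on to doubt the primary result. The documents do not support that: the primary analysis is on ITT, which this list does not alter, and PP may never be analysed.

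**What to change.** 1. **Item 07.** Restrict it to subjects on three-times-weekly dialysis, since others may attend at any session. Apply it to the Week -2, Day 1 and Day 29 Hgb visits, and to Day 15 only where that value is used to impute Day 29.
2. **Dry-weight check.** Keep it, and state whether it is a condition of exclusion.
3. **Item 03, CYP2C8.** For PP purposes, end the window at the Hgb sample used for the primary value. The protocol prohibition is unchanged.
4. **Item 03, epoetin.** Ask the sponsor to reconcile the two clauses, since the second never acts.

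The cost is a few lines of SAP wording before unblinding. Item 07 already requires dialysis session to be worked out for Days 15 and 29; the same must be done for Day 1 and Week -2. SAP Listing 55 shows dialysis data from a Day 1 history form and from on-study forms, so the Week -2 session may have to be inferred from visit date and schedule.
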